## 6.5 WINDOWING CONVENTIONS

No visit windowing will be performed in the statistics for this study.

## 6.6 STATISTICAL TESTS

The default significant level will be 2-sided 0.1; confidence intervals (CI) will be 90% and

Document:

\leedc-vnasc01\Biosdata\Reistone\SHR0302\CZA55021\Biostatistics

Author:

[REDACTED]

Version Number:

Final v1.2

Version Date:

23Mar2021

Template No: CS\_TP\_BS016 Revision 5  
Effective Date: 01Apr2018

Reference: CS\_WI\_BS005

statistical tests will be two-sided, unless otherwise specified in the description of the analyses.

## 6.7 COMMON CALCULATIONS

- For quantitative measurements, change from baseline will be calculated as:  
Change from baseline =Test Value at Visit X – Baseline Value
- For quantitative measurements, percent change from baseline will be calculated as:  
Percent change from baseline=  $((\text{Test Value at Visit X} - \text{Baseline Value}) / \text{Baseline Value}) * 100$

## 6.8 SOFTWARE VERSION

All analyses will be conducted using SAS version 9.4 or higher.

## 7. STATISTICAL CONSIDERATIONS

### 7.1 MULTICENTRE STUDIES

This study will be conducted by multiple investigators at multiple centers internationally.

### 7.2 MISSING DATA

In general, missing values will not be imputed for descriptive statistics.

Unless otherwise specified, all analysis will be based on the number of observations in the relative population, i.e. patients with missing information will be included in the denominator when calculating percentages.

Missing efficacy data will be handled as described in section 15.1 and 15.2.2 of this analysis plan.

Missing or incomplete data will not be imputed unless indicated otherwise.

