1.3 Study Design

This is an 8+8 weeks, randomized, double-blind, multi-center, placebo controlled, parallel group study to include adult patients with moderate to severe active Ulcerative Colitis. The study consists of an 8-week blinded treatment phase, followed by 8-week of blinded active arms extension phase. The primary endpoint is assessed at the end of treatment phase at week 8.

Eligible subjects will be randomized to either one of the 3 doses of active drugs or placebo in 1:1:1:1 ratio for 4mg QD, 4mg BD, 8mg QD and placebo group respectively for treatment phase. The total number of subjects to be randomized is 152. There will be a total of 9 outpatient clinic visits. Subjects randomized into placebo in treatment phase will also have a pre-assigned randomized treatment sequence for extension phase, which are 3 active groups (placebo -> 4mg QD, placebo -> 4mg BD, and placebo -> 8mg QD) in a 1:1:1 ratio. Subjects randomized to the active arms for treatment phase will remain in the same dose group in the extension phase.

At Visit 1 (screening), subject will be screened and if the subject meets the inclusion/exclusion criteria, the subject can be consented and enrolled into the study with a subject identifier number.

At Visit 2 (Day 0), subject will be randomized into the study if there is no further change to subject's criteria.

After randomization, the subject will be followed-up at week 1, week 4, and week 8, corresponding to Visit 3, Visit 4, and Visit 5 at treatment phase respectively. At Visit 5 (week 8) the primary endpoint assessment will be conducted. Following this treatment phase, subjects have the option to enroll into a further 8 weeks of active arms extension phase.

All subjects that have completed the initial 8 weeks (non-responders or responders) have the option to enter a blinded active arm 8-week extension phase according to the group they were randomized to for extension phase. All subjects have the option not enrolling into the extension phase after first 8 weeks of treatment. All subjects in the extension phase are followed-up for further 2 weeks until week 18 (last visit). Subjects who have completed the first 8-week of treatment phase, but decided not entering into extension phase are required to attend the 2-week follow-up visit. Early withdrawn subjects during the first treatment phase cannot enter the extension phase.

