## 5.5 SAFETY ANALYSIS SET [SS]

The Safety analysis set will comprise all patients who received any amount of investigational product and will be based on the actual treatment received, if this differs from that to which the patient was randomized to. The Safety analysis set will be used for all summaries of safety data.

If there is any doubt whether a patient was treated or not, they will be assumed treated for the purposes of analysis.

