## 8. OUTPUT PRESENTATIONS

Appendix 1 of the analysis plan shows conventions for presentation of data in outputs.

The templates provided with this SAP describe the presentations for this study and therefore the format and content of the summary tables, figures and listings to be provided by ██████████ Biostatistics.

Continuous variables will be summarized using descriptive statistics, i.e., non-missing observations, mean, median, standard deviation (SD), minimum, and maximum.

Categorical variables will be summarized by counts and percentages. Unless otherwise stated, the calculation of proportions will be based on the population of interest. Counts of missing observations will be included in the denominator, unless specified.

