### 16.3 LABORATORY EVALUATIONS

Results from the central laboratory will be included in the reporting of this study for Hematology, Chemistry, Urinalysis and Others. All laboratory assessments will be listed in the outputs.

Presentations will use SI Units. All laboratory data will be summarized and listed for all patients in the SS set by visits where data are collected.

Quantitative laboratory measurements reported as “< X”, i.e. below the lower limit of quantification (BLQ), or “> X”, i.e. above the upper limit of quantification (ULQ), will be converted to X for the purpose of quantitative summaries, but will be presented as recorded, i.e. as “< X” or “> X” in the listings.

Quantitative laboratory measurements will be compared with the relevant laboratory reference ranges in SI units and categorized as:

- Low: Below the lower limit of the laboratory reference range.
- Normal: Within the laboratory reference range (upper and lower limit included).
- High: Above the upper limit of the laboratory reference range.

The following summaries will be provided for laboratory data:

- Actual and change from baseline by visit (for quantitative measurements)
- Incidence of abnormal values according to normal range criteria
- Shift tables representing categorical change of laboratory evaluation results from baseline to each post baseline
- Listing of patients with laboratory results

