## 16.5 VITAL SIGNS

The following Vital Signs measurements will be reported for this study:

- Systolic Blood Pressure (mmHg)
- Diastolic Blood Pressure (mmHg)
- Heart Rate (beats/min)
- Temperature (°C)
- Weight
- Height

The following summaries will be provided for vital signs data:

- Actual and change from baseline by visit
- Incidence of abnormal values according to markedly abnormal criteria
- Listing of patients with vital signs measurements

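### By-visit abnormality and shift percentages for laboratory, ECG and vital-sign data are diluted by patients with no value, because the SAP's default denominator is not overridden for these tables

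*SAP*

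**What the plan says.** SAP 7.2 sets a rule that holds unless a section says otherwise: "patients with missing information will be included in the denominator when calculating percentages". SAP 8 repeats it for categorical summaries: "Unless otherwise stated, the calculation of proportions will be based on the population of interest", and then "Counts of missing observations will be included in the denominator, unless specified". The same section bases continuous summaries on non-missing observations.

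For safety data the population is broad. SAP 5.5 states: "The Safety analysis set will comprise all patients who received any amount of investigational product". No post-baseline measurement is required.

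The safety sections then list their outputs:

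- **SAP 16.3 (laboratory):** "All laboratory data will be summarized and listed for all patients in the SS set by visits where data are collected". The outputs include "Incidence of abnormal values according to normal range criteria" and shift tables from baseline to post-baseline results.
- **SAP 16.4 (ECG):** incidence of abnormal values and a shift table of the overall interpretation to each time point. SAP 16.4.1 adds categories of the maximum QTcF.
- **SAP 16.5 (vital signs):** "Incidence of abnormal values according to markedly abnormal criteria".

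None of these gives a denominator of its own. Protocol 9.3.4.4 also has laboratory, vital-sign and ECG data summarised at each scheduled time point, with frequency tables for categorical outcomes.

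On who will have a value, Protocol 1.3 says "All subjects have the option not enrolling into the extension phase after first 8 weeks of treatment" and bars early withdrawals from the extension. SAP 3.1 allows for 8% dropout.

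**The concern.** Keeping patients without data in the denominator is right for two kinds of result: adverse-event incidence, where every treated patient is at risk, and binary efficacy endpoints, where the plan deliberately counts non-completers as failures. It does not suit a measured safety variable at a given visit. A patient with no haemoglobin at Week 12 is neither normal nor abnormal there, yet enlarges the denominator and cannot enter the abnormal count.

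The SAP also becomes inconsistent within a single visit. The mean of a laboratory parameter would rest on those measured, while the percentage abnormal for the same parameter would rest on the whole arm.

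SAP 16 plans no statistical comparison of safety data unless a section says otherwise, so readers will judge the doses from these descriptive percentages. Safety and tolerability is a secondary objective (SAP 2.2), and SAP 3.1 says the trial's data are to support the choice of one or two doses.

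**Working it through.** **Inputs from the documents.** 152 randomised 1:1:1:1, so 152 / 4 = 38 per arm; 8% dropout; 35 evaluable per arm, 140 in all (Protocol 1.3 and 9.2.1, SAP 3.1). Under Protocol 5.12, laboratory tests fall at every visit, including Weeks 9, 12 and 16. ECGs in the extension fall at Weeks 9 and 16.

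**Assumptions, not in the documents.** Extension uptake of 60–90% among those who complete Week 8; a 20% abnormality rate among measured patients; no other missed visits and no losses during the extension.

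**The plan's own figures.** 152 × 0.92 = 139.8, against 140 stated. Per arm, 38 × 0.92 = 34.96, against 35 stated. The documents give no expected abnormality rate, so there is none to reproduce.

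**Formula.** Let N be the patients in the column, k those with a value and a those abnormal. The rate among measured patients is r = a / k, and the missing share is m = 1 − k / N. The SAP default prints a / N = r × (k / N) = r × (1 − m). The relative understatement is therefore m.

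**Week 8, planned dropout only.** m = 0.08, so 0.20 × 0.92 = 18.4%. In whole patients, 7 abnormal of 35 measured is 20.0%, and 7 of 38 is 18.4%.

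**Extension visits.** Share measured = 0.92 × uptake.

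| Assumed uptake | Measured of 38 | m | 20% prints as |
|---|---|---|---|
| 60% | 21.0 | 44.8% | 11.0% |
| 70% | 24.5 | 35.6% | 12.9% |
| 80% | 28.0 | 26.4% | 14.7% |
| 90% | 31.5 | 17.2% | 16.6% |

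**Unequal missingness (illustration).** Suppose two arms each have 20% abnormal among measured patients, with 90% and 65% measured. They print as 0.20 × 0.90 = 18% and 0.20 × 0.65 = 13%. The 5-point gap comes entirely from the denominator.

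**Worst-value tables.** For maximum QTcF, or any table that counts a patient once over all post-baseline values, m is only the share with no post-baseline value at all. Early visits and the early-withdrawal assessments should keep that share small.

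**The case against.** The strongest reply is that the text reviewed is not the whole specification. Both rules yield where something else is specified, and SAP 8 says that templates supplied with the SAP define the tables. Those templates could set a by-visit denominator or print a missing row, from which a reader could recover the measured-patient rate. This stands as a limit on what can be said about the final tables. It does not remove the point: the SAP text states a rule that gives a misleading figure, and the correction belongs where the rule is.

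Several narrower objections also stand:

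- The abnormal-value lines in SAP 16.3 to 16.5 do not themselves say by visit. The outputs explicitly tied to visits or time points are chiefly the laboratory and ECG shift tables, although SAP 16.3 has all laboratory data summarised by visit.
- Completers who decline the extension must still attend the 2-week follow-up visit, where these data are collected. They are therefore not missing from every later assessment.
- SAP Appendix 1 defines separate columns for placebo patients by the dose taken after the treatment phase. The figure of 38 thus describes the active arms, not every column.
- During the placebo-controlled period, using the documented dropout, the effect is 1.6 percentage points, or 0.016 × 38 = 0.6 of a patient.

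A reader might infer that the arm losing most patients to toxicity will look safest, and that measured-patient denominators would cure this. The documents do not support that. A patient stopped for toxicity is absent from later visits under either rule. The planned tables of adverse events, serious events and discontinuations, together with the early-withdrawal measurements, are what reveal such losses.

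**Conclusion.** The point holds for categorical safety tables shown by visit: laboratory and ECG shift tables, and abnormal-value incidence wherever it is tabulated by visit. On the visible text, these percentages are understated by a relative amount equal to the share of patients with no value, and unequal missingness between arms produces a spurious difference.

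The only size that rests on a documented figure is small: 20% becomes 18.4% at 8% dropout. Because the extension is optional and closed to early withdrawals, the dilution must be at least as large at Weeks 9, 12 and 16, and larger as soon as any completer declines. The range of about 11–17% depends wholly on the assumed 60–90% uptake.

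Two broader readings are tempting and go too far. One is that every percentage in the report is diluted. Adverse-event incidence, the primary analysis and the endpoints that count non-completers as failures use the appropriate denominator, and worst-value tables lose only patients with no post-baseline value. The other is that much of each extension column will certainly be empty. The documents give no uptake figure, so that cannot be asserted.

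This should be corrected before the safety tables are produced. It does not affect alpha, sample size or the primary conclusion.

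**What to change.** Add one paragraph to SAP 16.3 to 16.5:

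- For categorical and shift tables of laboratory, ECG and vital-sign data by visit, the denominator is the number of safety-set patients in that study phase with a value at that visit. Shift tables and criteria based on change also require a baseline value.
- For worst or maximum post-baseline tables, the denominator is the number of patients with at least one post-baseline value.
- The n used is printed in each column.
- The SAP 7.2 default continues to apply to adverse-event incidence and to endpoints that count non-completers as failures.

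If the templates already do this, the paragraph only brings the text into line with them.

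The cost is the paragraph and a change to the table shells, with no new data. The drawback is that denominators will vary by visit. The change does not remove informative dropout, so the tables must still be read with the discontinuation and treatment-emergent adverse-event tables.

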## 7.3 EXAMINATION OF SUBGROUPS

Subgroup analyses for primary endpoint will be conducted as exploratory analysis. It should be noted that the study was not designed to detect response differences with high statistical power within subgroups. Forest plots will be used to display differences in clinical response rate across subgroups in each SHR0302 dose level compared to placebo group.

The following subgroups will be assessed and described:

- Age (years)
  - < 45 years
  - ≥ 45 years
- Sex
  - Male
  - Female
- Country
  - USA
  - Ukraine
  - Poland
  - China
- Ethnicity Origin
  - Not Hispanic or Latino
  - Hispanic or Latino
  - Not reported or Unknown
- Duration of UC (years)
  - < 5
  - ≥ 5
- Overall Compliance before Week 8

- Yes ( $\geq 80\%$  compliance)
  - No ( $< 80\%$  compliance)
- Previous exposure to anti-TNF $\alpha$ /biological treatment
  - Yes
  - No
- Baseline total Mayo score
  - $\leq 10$
  - $> 10$

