### 13.1 DERIVATIONS

- Duration of exposure(days)= Last date of exposure in corresponding phase– First dose date in corresponding phase +1

When the start or stop date is missing, then the exposure will be treated as missing. Interruptions, compliance, and dose changes are not taken into account for duration of exposure.

- Planned number of tablets

The investigational product taken during the 16-week treatment period will be double blind. In order to preserve blinding and ensure patients compliance, all arms are administered under twice daily dosing regime and placebo is used according to the schedule in table 1. At each dosing time (morning, am or afternoon, pm), patient will be taking two tablets. The treatments are given twice daily and it is assumed that the patient should take medication from the morning of the visit day at which their medication is initially dispensed to the afternoon of their last visit date. At each dosing time (morning, am or afternoon, pm), patient will be taking two tablets. In one day, a patient will take a total of four tablets, two tablets in the morning and two tablets in the afternoon. For example, if the initial dispense date is Day 1 and the last visit date is Day 10, then the patient should have taken 2 tablets at am on Days 1 to 10; hence, the total number of planned tablets at am would be  $10 \times 2 = 20$ .

- Actual number of tablets=Sum of tablets captured on Patient Diary
- Number of dosing days= Last date of exposure in corresponding phase – First dose date in corresponding phase +1(-off drug period)

Number of dosing days is the number of days with non-zero tablets.

- Cumulative dose (mg)= Sum of SHR0302 dose based on Patient Diary.

In one day, a patient will take a total of four tablets, two tablets in the morning and two tablets in the afternoon. According to treatment arm and the time of dosing, the average dose of SHR0302 per tablet are calculated and listed in below table (Table 1).

According to the actual treatment group of a patient, SHR0302 dose per day will be calculated by the following formula:

SHR0302 dose per day=number of tablets taken at am\* average SHR0302 dose per tablet (am) +number of tablets taken at pm\* average SHR0302 dose per tablet (pm)

Cumulative dose will be sum of SHR0302 dose per day based on Patient Diary.

Table 1: Study drug packaging design and average dose per tablet

Study Arms-all BID	Dose 1(am)	Average dose per tablet (am)	Dose 2 (pm)	Average dose per tablet(pm)

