## 14. STUDY MEDICATION COMPLIANCE

Compliance to investigational product will be presented for the SS. Compliance with investigational product is derived from data recorded on the eCRF “Drug Accountability” and “Noncompliance With Study Treatment” pages. Compliance will be calculated as the number of tablets taken (amount dispensed-amount returned-amount lost) divided by the planned number of tablets to be taken. The compliance rate will be categorized as <80 , ≥80 to ≤100 and >100. Compliance in treatment phase and extension phase will be summarized and

Document: \\ieedc-vnasc01\Biosdata\Reistone\SHR0302\CZA55021\Biostatistics  
Author: [REDACTED]

Version Number:  
Version Date:

Final v1.2  
23Mar2021

Template No: CS\_TP\_BS016 Revision 5  
Effective Date: 01Apr2018

Reference: CS\_WI\_BS005

presented. Furthermore, Compliance will be calculated for kits dispensed at baseline, Week 4, Week 8, Week 12, other visits, unscheduled visit and overall. Overall Compliance before Week 8 used in subgroup analysis in section 7.3 is defined as taking more than or equal to 80% of study drug products before Week 8. Overall Compliance before Week 8 will be calculated as the total number of tablets taken before Week 8 divided by the planned number of tablets to be taken before Week 8.

In addition, the following information will be summarized:

- Overall non-compliance

Overall non-compliance is defined as taking less than 80% of study drug products as directed by the dosing instructions.

- Reason for non-compliance with study treatment

A by-patient listing will include any reasons for noncompliance with study treatment.

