For clinical response at week 8, the comparisons of the percentage of patients achieving clinical response in each treatment versus placebo will be made using a stratified Cochran-Mantel-Haenszel (CMH) test with stratification according to prior anti-TNF $\alpha$ /biological treatment (with or without). The CMH method is a technique that generates an estimate after adjusting for or taking into account stratification. Strata-adjusted proportion difference between each SHR0302 dose group and placebo group will be obtained by CMH method [1].

Missing data will be imputed as NCF. If a patient is missing one or more Mayo subscores at the visit where the endpoint is being assessed, the patient would be considered a treatment failure.

Two-sided p-values for the treatment group differences will be provided for all comparisons. Thus, 3 p-values will be gained. Order the three p values as  $(p_{(3)}, p_{(2)}, p_{(1)})$ , where  $p_{(3)} \geq p_{(2)} \geq p_{(1)}$ . The decision rules are provided in Figure 2. Note that in Figure 2,  $H_{(01)}$  is the

corresponding null hypothesis of the smallest p value  $p_{(1)}$ ,  $H_{(02)}$  is the corresponding null hypothesis of the second smallest p value  $p_{(2)}$ , and  $H_{(03)}$  is the corresponding null hypothesis of the largest p value  $p_{(3)}$ . Therefore,  $H_{(01)}$  and  $H_{01}$  may not be the same null hypothesis,  $H_{(02)}$  and  $H_{02}$  may not be the same null hypothesis,  $H_{(03)}$  and  $H_{03}$  may not be the same null hypothesis, either.

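### The primary-endpoint forest plots include compliance up to Week 8, a post-randomisation factor that can show effect modification where there is none

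*SAP*

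**What the plan says.** SAP 7.3 specifies the display: "Forest plots will be used to display differences in clinical response rate across subgroups in each SHR0302 dose level compared to placebo group". Seven of the eight factors are fixed before dosing: age, sex, country, ethnicity, disease duration, previous anti-TNFα/biological exposure and baseline total Mayo score. The eighth is "Overall Compliance before Week 8", split at 80%.

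SAP 14 ties its definition to this plot: "Overall Compliance before Week 8 used in subgroup analysis in section 7.3 is defined as taking more than or equal to 80" per cent of study drug. It computes the value as "the total number of tablets taken before Week 8 divided by the planned number of tablets to be taken before Week 8". SAP 13.1, the section that says how planned tablets are counted, runs the count "from the morning of the visit day at which their medication is initially dispensed to the afternoon of their last visit date".

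For the primary endpoint, SAP 15.1.1 states "Missing data will be imputed as NCF". A patient missing any Mayo subscore at the assessed visit is a treatment failure. SAP 3.3 confirms that some subjects have no Week 8 result.

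The only cautions in SAP 7.3 apply to every factor alike: "Subgroup analyses for primary endpoint will be conducted as exploratory analysis", together with a note that the study was not designed for high power within subgroups.

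**The concern.** There are two separate problems.

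**Selection.** Whether a patient takes 80% of the tablets can depend on the assigned arm, through tolerability, lack of response or the discontinuation criteria in Protocol 5.6 and 5.9. Patients on a dose who stay above 80% need not be comparable with placebo patients who do so. This holds whatever the missing-data rule.

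**A link to the outcome.** Stopping early lowers compliance, and it can also leave no Week 8 score, which counts as failure. Three provisions strengthen the link:
- Protocol 6.5 lets the investigator withdraw a patient for non-compliance, using the same 80% cut.
- Protocol 5.8 asks for endoscopy at early withdrawal only if feasible.
- The SAP applies no visit windowing (6.5) and lists early withdrawal as its own visit (Appendix 1), so a withdrawal score does not become a Week 8 score.

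At stake is interpretation. The compliance rows appear in the same format as valid baseline subgroups, and a gap between them could be read as the drug working better in patients who take it.

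**Working it through.** **Plan's own figures.** With 35 per arm, rates of 57%, 57%, 50% and 30%, and Hochberg at two-sided 0.1, simulation of 400,000 trials gives global power of 80.05% (pooled z) and 80.2% (unstratified CMH). The plan states 80%. For sample size, 140/0.92 = 152.2 against the stated 152, or 38 per arm. None of this depends on the subgroup list.

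**Who can reach 80%.** SAP 13.1 gives the daily amount: "In one day, a patient will take a total of four tablets".
- *Eight-week denominator* (the natural reading of SAP 14): 4 × 56 = 224 tablets; 0.80 × 224 = 179.2 tablets; 179.2/4 = 44.8 days. A patient on the planned daily amount who stops before about day 45 cannot reach 80%.
- *Last-visit denominator* (SAP 13.1): a patient who takes every tablet and is seen on the last dosing day scores 100%. SAP 3.1 allows the withdrawal visit up to 2 weeks later. A stop at week w then scores w/(w + 2), from 1/3 = 33% at week 1 to 6/8 = 75% at week 6.

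The same withdrawer can therefore fall in either row, depending on the denominator and the visit date.

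**Size of the artefact.** Inputs from the SAP 3.1 sample-size paragraph are p = 57% (active), p = 30% (placebo) and dropout d = 8%. Assumptions not in the documents:
- completer response is the same whatever the compliance, so there is no true effect modification;
- dropout is equal in both arms, and every dropout is a failure;
- all 38 per arm are in the FAS;
- a fraction f of dropouts, and a fraction c of completers, are below 80%.

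Response rates for each arm:
- below 80%: (1−d)·c·p / [d·f + (1−d)·c]
- at least 80%: (1−d)(1−c)·p / [d(1−f) + (1−d)(1−c)]
- overall: (1−d)·p, a difference of 0.92 × 27 = 24.8 points

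Worked case, f = 1 and c = 5%. The below-80% factor is 0.046/(0.08 + 0.046) = 0.365. The rates are 0.365 × 57 = 20.8% and 0.365 × 30 = 11.0%, a difference of 9.9 points before rounding. The row holds 38 × 0.126 = 4.8 patients per arm.

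| Dropouts below 80% (f) | Completers below 80% (c) | Difference, ≥80% row | Difference, <80% row | Patients per arm, <80% row |
|---|---|---|---|---|
| all | 0% | 27.0 | 0.0 | 3.0 |
| all | 5% | 27.0 | 9.9 | 4.8 |
| all | 10% | 27.0 | 14.4 | 6.5 |
| half | 0% | 25.9 | 0.0 | 1.5 |
| half | 5% | 25.8 | 14.4 | 3.3 |
| half | 10% | 25.8 | 18.8 | 5.0 |
| none | 5% | 24.7 | 27.0 | 1.7 |
| none | 10% | 24.6 | 27.0 | 3.5 |

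Unequal dropout changes the picture again. With an assumed 5% on active and 16% on placebo, c = 5% and f = 1, the rows show 27.0 and 21.5 points.

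**The case against.** The case for leaving the plan alone has four parts.

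1. **The analysis is exploratory.** SAP 7.3 says so, warns of low power, and specifies no interaction test. This stands, and it keeps the point small. But low power and loss of randomised comparability are different problems, and the caution addresses only the first.

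2. **The link to the non-completer rule is incomplete.** This stands. A reader might infer that the below-80% row must show zero response and zero difference by construction. The documents do not support that. On the SAP 13.1 count, a withdrawer seen promptly can score 80% or more. A fully compliant patient missing one Week 8 subscore is a failure in the compliant row. Completers below 80% can exist, since withdrawal for non-compliance is discretionary, and they can respond. Zero is one end of the range.

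3. **The shift is small against the noise.** In the extreme case the compliant row moves from 24.8 to 27.0 points. The unstratified 90% Wald half-width at 35 per arm is 1.645 × √[(0.57 × 0.43 + 0.30 × 0.70)/35], about 19 points. This is fair for that row. The visible contrast would come from the other row, which holds a handful of patients and is too sparse to inform anyone.

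4. **Deleting the factor loses something.** This also stands. SAP 14 reports compliance, but not response by compliance.

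**Conclusion.** The point holds as one of labelling and interpretation. Compliance up to Week 8 is a post-randomisation factor placed unmarked among baseline subgroups, and differences within its levels are not randomised comparisons. That conclusion needs no numerical assumption.

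The added artefact from counting non-completers as failures is possible, but its size cannot be settled from the documents. Under the assumptions shown, it runs from 27.0 points against 0 to 14.4 when all dropouts are below 80%, to about 25 against 27 when none are. The plot can therefore suggest effect modification that does not exist; it would be too strong to say that it will, or that readers will see an effect confined to compliant patients. The primary test, alpha, power and sample size are not touched. It is a minor but worthwhile correction.

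**What to change.** Remove compliance from the SAP 7.3 subgroup list and from the forest plots. Edit the sentence in SAP 14 that defines the variable for SAP 7.3, and any output template that carries the row.

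If response by compliance is still wanted, give it in a separate descriptive table by arm, labelled post-randomisation and non-causal. State there whether planned tablets run to Week 8 or to the last visit.

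The cost is a few lines of SAP text and possibly one template. The real downside is that the forest plot no longer shows response by compliance, which SAP 14 does not otherwise report; the separate table recovers it.
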